**CL in Pregnancy:** Three studies have been done in this field, all with crossover designs. (1) The Deltec Cozmo insulin pump and FreeStyle Navigator CGM (HCL system with a model predictive control algorithm) was worn by 10 women for 24 hours at a time at 14.8 and 28 weeks gestation. Plasma TIR (63-140 mg/dL) overnight increased (84% early to 100% in late gestation,  $p=0.09$ ), though nocturnal hypo- and hyperglycemia did not change. (2) The Animas 2020 Insulin Pump with FreeStyle Navigator CGM or CSII alone was used for 24 hours at a time at 19 and 23 weeks gestation ( $n=12$ ). Hypoglycemia was significantly reduced with HCL wear (time spent  $<45$  mg/dL, lower low blood glucose index, and fewer hypoglycemic episodes), but overnight plasma TIR was similar in both groups. Overall, both sessions were in the plasma TIR 81% of the time. (3) Finally, 16 women were randomly assigned to HCL therapy (DANA Diabecare R Insulin Pump with FreeStyle Navigator II CGM) or SAPT (control condition) for 4 weeks of over-night use then crossed over after a washout period. Women were then allowed to continue HCL therapy, if they wanted to do so. The HCL system used was investigational and utilized a model predictive control (MPC) algorithm^34. Semi-structured interviews and validated questionnaire data from this study showed that HCL wear was associated with some modest benefits with respect to quality of life (feelings of better glucose control/excitement/empowerment and less worry about hypoglycemia occurring overnight) but also concerns about device visibility and varying degrees of attention to data and hypo-/hyperglycemia symptoms. Time spent  $<63$  mg/dL was low in both groups (1.9% HCL vs 1.8% SAPT,  $p=0.67$ ). HCL wear significantly increased TIR (66.3% HCL vs 56.8% SAPT,  $p<0.001$ ), decreased time  $>140$  mg/dL (31.6% HCL vs 40.9% SAPT,  $p<0.001$ ) and  $>180$  mg/dL (12.6% HCL vs 17.3% SAPT,  $p=0.001$ ), and lowered mean glucose (128 mg/dL HCL vs 137 mg/dL SAPT,  $p<0.001$ ). After crossover, 87.5% (14/16) of the women continued using HCL therapy until delivery. There were 26 adverse events (skin reactions and minor illnesses) and 95 device deficiencies with no differences between groups. Serious adverse events were unrelated to the devices. For the 24 hours prior to delivery the median glucose level was 110 mg/dL (86.8% TIR). Adverse outcomes were: 5 cases of pre-eclampsia, 15 cesarean section deliveries (10 prior to onset of labor), 7 deliveries  $<37$  weeks gestation, 13 LGA infants (birth weight  $>90^{\text{th}}$  percentile), 14 infants with neonatal hypoglycemia, and 12 cases of neonatal intensive care admissions. Thus, hypoglycemia was reduced with one and TIR increased with two out of the three HCL systems. None of the HCL systems studied are approved in the United States. No HCL system has been compared to SAPT for the duration of a pregnancy and early post-partum or has been shown to improve maternal and fetal outcomes. None of the HCL systems studied in pregnancy used a PID control algorithm, which may perform differently

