To address **Specific Aim 1**, we will compare percent of time spent in the SH range of <54 mg/dL on CGM (primary outcome) using a non-inferiority t-test with a margin of 1%. Counts of DKA and adverse skin reactions (secondary outcomes) will be compared between groups (HCL vs. SAPT) using t-tests for normally distributed variables and Wilcoxon Rank-Sum test for non-normal variables. As the purpose of this study is to demonstrate that HCL has a similar safety profile compared to SAPT during pregnancy, we will use a non-inferiority test. As a secondary analysis of events such as SH, DKA, and skin reactions, we will account for potential differential follow-up times due to miscarriage, drop-out, and withdrawal using Poisson regression with an offset for follow-up time. To address **Specific Aim 2**, we will compare CGM glucose variables (primary outcomes for glucose variables will be time spent <54, <63, 63-140, >140, >180 mg/dL; secondary outcomes will be glucose SD, J index, HBGI, LBG, MAGE, and CONGAn) and fear of hypoglycemia score between groups (HCL vs. SAPT) using t-tests for normally distributed variables and Wilcoxon Rank-Sum test for non-normally distributed variables. We will examine the buckets of time spent in each range (hypoglycemia, in range, and hyperglycemia) by day and night, as well as day-to-day variation. Mean glucose variables and hypoglycemia fear scores will be compared during each trimester of pregnancy and 4-6 weeks post-partum using mixed models. To address **Specific Aim 3**, we will compare SF-36 scores, insulin device satisfaction and glucose device satisfaction by group (HCL vs. SAPT) using t-tests if scores are normally distributed and Wilcoxon Rank-Sum test if scores are non-normal. We will analyze changes in INSPIRE Questionnaire scores over time in the HCL group. **Specific Aim 4** is an exploratory aim, and for this aim we will examine rates of fetal loss, preeclampsia, cesarean section, LGA, and neonatal hypoglycemia using Chi-square tests. We will account for potential differential follow-up times due to miscarriage, drop-out, and withdrawal using Poisson regression with an offset for follow-up time as a sensitivity analysis, in addition to the proposed chi-square tests in the exploratory analyses of fetal loss, preeclampsia, Caesarean section, LGA, and neonatal hypoglycemia. We will use mixed models to analyze changes in repeated measures, such as glycemia variables and hypoglycemia fear scores by trimester. We will evaluate the percent of time spent in closed loop by trimester as a feasibility outcome that is important to the next step of a larger clinical trial with efficacy outcomes.

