
For women who discontinue CGM therapy during the study, we will do an intention to treat analysis of above-stated outcomes. The alpha level will be 0.05 for all analyses, except the non-inferiority tests (alpha = 0.025). The use of mixed models and Poisson regression will allow for analysis of data for the portion of the study completed with CGM therapy.

**Power and Sample Size Calculations:** The primary outcome for **Specific Aim 1** is percent of time spent <54 mg/dL on CGM. With a sample size of 10 women per group (20 study completers), we will have 80% power to detect non-inferiority using a one-sided alpha of 0.025 and a non-inferiority margin of 1.5% of time spent <54 mg/dL for HCL compared to SAPT, using estimates of variability from the PI's current study of CGM use during pregnancy. The standard deviation of time spent <54 mg/dL based on data from the PI's current study of CGM use during pregnancy was 1.1%. For **Specific Aim 2**, with a sample size of 10 women per group (20 study completers), we will have 83% power to detect a difference in time spent in target glucose range (65-140 mg/dL, this range was used in the power calculations because at that time there was no consensus on optimal time in range in pregnancy) of 3.3 hours/day (13.8%) between HCL to SAPT, assuming a standard deviation of 2.5 hours/day (effect size=1.0 SD). This is similar to effect sizes reported in another artificial pancreas study showing a difference of 2.5 hours/day (10.4%) between groups and a study of HCL in pregnancy (in a crossover design) showing a difference of 3.6 hours/day (15.2%). While this study is not powered to detect significant differences in maternal-fetal outcomes as described in **Specific Aim 4**, our goal is to provide estimates and preliminary data on these outcomes to inform the sample size needed for a larger trial focused on these outcomes, once the safety of the HCL system in pregnancy has been established.

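### Aim 4's Poisson sensitivity analysis uses a follow-up-time offset for cesarean section, LGA and neonatal hypoglycemia, which are settled at delivery, so follow-up time is not exposure

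*Combined protocol and SAP*

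**What the plan says.** Section F, Statistical Analysis Plan, Specific Aim 4, gives the main analysis: "we will examine rates of fetal loss, preeclampsia, cesarean section, LGA, and neonatal hypoglycemia using Chi-square tests". For the same list, the "exploratory analyses of fetal loss, preeclampsia, Caesarean section, LGA, and neonatal hypoglycemia", it then adds a second approach, "using Poisson regression with an offset for follow-up time as a sensitivity analysis". The reason given is unequal follow-up caused by miscarriage, drop-out and withdrawal.

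The Specific Aim 1 text uses the same device for severe hypoglycemia (SH), diabetic ketoacidosis (DKA) and skin reactions: "we will account for potential differential follow-up times due to miscarriage, drop-out, and withdrawal". Those events can recur and do accrue over time.

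Three things are left open for Aim 4: when follow-up starts and stops for the offset, which variance estimator is used, and how women without a delivery outcome enter the model. Multiple pregnancies are excluded (Inclusion/Exclusion Criteria), so each of the five outcomes occurs at most once per woman. The power section says the study is not powered for these outcomes, but that their estimates should inform the size of a larger trial.

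**The concern.** An offset for log follow-up time turns the modelled quantity into events per unit time. That is meaningful when the event can happen in any week observed. Cesarean section and neonatal hypoglycemia cannot occur before delivery, and LGA is classified at birth, already relative to gestational age. The weeks between randomization and delivery carry no risk of these outcomes, and delivery itself fixes how many such weeks there are.

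Three consequences follow for these outcomes:

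- Earlier delivery in one arm reads as a higher rate even when the proportion affected is identical.
- Women lost before delivery contribute either nothing or event-free time that was never at risk, so the stated purpose of the offset is not met.
- A Poisson model sets the variance equal to the mean, which is too large for a common yes/no outcome unless a robust variance is used.

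The stake is the use of the results. The chi-square tests give no interval. The Poisson model is the only named Aim 4 method that yields an effect ratio with a confidence interval, which is what the designers of a larger trial would look for.

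**Working it through.** The plan states no rate, standard error or power for this analysis, so there is no figure of its own to reproduce.

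**Inputs from the documents**
- Sample size: "With a sample size of 10 women per group (20 study completers".
- Level: "The alpha level will be 0.05 for all analyses, except the non-inferiority tests (alpha = 0.025". Sidedness is not stated; two-sided 5% is assumed.
- Event rates from the 16-woman closed-loop study described in Background and Significance: "15 cesarean section deliveries (10 prior to onset of labor", so 15/16; "14 infants with neonatal hypoglycemia", so 14/16; LGA 13/16; preeclampsia 5/16.
- Randomization at the start of the 2nd trimester; study follow-up to 6 weeks post-partum.

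**Assumptions**
- Follow-up counted from week 14 in steps 1 and 2.
- Delivery at 37 versus 35 weeks in step 1.
- Fetal loss rate of 2% to 10%.

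**Step 1. Effect of the offset at equal risk.** With risk p in both arms, the expected rate is p/T, so the rate ratio for the earlier-delivering arm is T(later)/T(earlier).
- Follow-up ending at delivery: (37 − 14)/(35 − 14) = 23/21 = 1.10.
- Follow-up ending 6 weeks post-partum: (37 − 14 + 6)/(35 − 14 + 6) = 29/27 = 1.07.
- A four-week difference (38 versus 34 weeks, counted from week 13): 31/27 = 1.15 to 6 weeks post-partum, or 25/21 = 1.19 to delivery.

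**Step 2. Women lost before delivery (assumed figures).** Take 10 women per arm, a 90% cesarean risk among women delivering at week 37, follow-up from week 14 to delivery, and two women in one arm withdrawing at week 26.
- Full arm: 9 expected events over 10 × 23 = 230 weeks.
- Other arm, withdrawn women kept as event-free: 0.9 × 8 = 7.2 events over 8 × 23 + 2 × 12 = 208 weeks. Ratio (7.2/208)/(9/230) = 0.88, although the risk is identical.
- Withdrawn women left out: 7.2/184 against 9/230, ratio 1.00. Here the offset has corrected nothing; the comparison is simply of proportions among women who delivered.

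**Step 3. Standard error of the log ratio, 10 per arm, equal risk p.** Model-based Poisson: √(2/(10p)). Binomial risk ratio: √(2(1 − p)/(10p)). The quotient is 1/√(1 − p).

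| Outcome | p | Poisson SE | Binomial SE | Quotient |
|---|---|---|---|---|
| Cesarean section | 15/16 | 0.462 | 0.115 | 4.00 |
| Neonatal hypoglycemia | 14/16 | 0.478 | 0.169 | 2.83 |
| LGA | 13/16 | 0.496 | 0.215 | 2.31 |
| Preeclampsia | 5/16 | 0.800 | 0.663 | 1.21 |
| Fetal loss (assumed) | 0.02 to 0.10 | – | – | 1.01 to 1.05 |

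At a 50% rate the quotient is 1.41. It reaches 2 only at a rate of 75%.

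Example with 9/10 events in each arm:
- Poisson SE √(2/9) = 0.471, 95% interval 0.40 to 2.52.
- Binomial SE √(2(1/9 − 1/10)) = 0.149, 95% interval 0.75 to 1.34.
- A Poisson fit with robust variance gives 0.149, the same as the binomial.

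**Step 4. Simulation.** There were 1,500 trials per rate with 10 per arm, delivery at mean 37 (SD 1.5) weeks (assumed), and follow-up from week 13 to 6 weeks post-partum. Mean model-based SE divided by the actual SD of the estimates was 2.18 (LGA), 2.76 (neonatal hypoglycemia) and 3.74 (cesarean). None of the 1,500 null trials was rejected for any of the three. With one arm delivering two weeks earlier at the same risk, the median rate ratio was 1.07 for all three. The point estimate does not depend on the variance estimator.

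**The case against.** The strongest reply is that little hangs on this. Aim 4 is labelled exploratory, the chi-square tests are its main analysis, the study claims no power for it, and the raw proportions needed to plan a larger trial are unaffected. The width error is conservative. The timing effect needs a between-arm difference in gestational age at delivery, which the documents do not predict, and 7% to 10% is small beside any interval from 10 women per arm. All of this stands, and it limits the weight of the point.

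The reply also blocks three stronger readings.

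- *All Aim 4 intervals are two to four times too wide.* The documents do not support this. The factor applies to three of five outcomes, at rates from 16 women using a different system, and only with model-based standard errors. The plan names no estimator, and a robust variance would remove the excess.
- *Person-time is wrong for every Aim 4 outcome.* Preeclampsia and fetal loss arise over gestation. A rate with time censored at the event is defensible for them and does address differential follow-up. That fetal loss ends follow-up is true of any first-event analysis.
- *Aim 4 cannot serve its purpose.* This treats a secondary check as the source of all its estimates.

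What the reply does not meet is the offset itself. For the three delivery outcomes, a robust variance repairs the width but leaves the ratio dependent on when women deliver. Pre-delivery losses also remain uncorrected.

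**Conclusion.** The point holds for cesarean section, LGA and neonatal hypoglycemia. For these, the offset makes an arm that delivers two weeks earlier appear to have a rate about 1.07 to 1.10 times higher at equal risk. That range assumes counting from week 14, and the end chosen depends on a follow-up definition the plan lacks. The offset also cannot adjust for women who leave before delivery.

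The inflation of the standard error by about 2.3, 2.8 and 4.0 times (LGA, neonatal hypoglycemia, cesarean) is conditional on model-based errors and on the cited rates of 13/16, 14/16 and 15/16. It is about 1.2 for preeclampsia at 5/16 and about 1.0 for fetal loss at the assumed rates.

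This is a stated method that misleads if followed. Its consequence is modest, but it should be corrected because Aim 4's estimates are meant to inform a larger trial.

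**What to change.** In the Specific Aim 4 text:

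1. For cesarean section, LGA and neonatal hypoglycemia, remove the follow-up-time offset. Report the risk difference and risk ratio among women who deliver, with exact or robust-variance intervals (a Poisson model with robust variance and no offset is one option).
2. Report fetal loss among all randomized women beside these results, with the number in each arm who have no delivery outcome, so that the denominator is visible.
3. Keep the person-time offset for SH, DKA and skin reactions. It may also stay for preeclampsia and fetal loss if time is censored at the event and the start and end of follow-up are defined.
4. Name the variance estimator wherever Poisson regression remains.

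The cost is a few sentences of SAP wording and no new data. One limitation should be acknowledged: restricting to women who deliver conditions on something that happens after randomization, which is why item 2 is needed.

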#### **IV. Research Methods**

##### **A. Outcome Measure(s):**

###### **Primary Outcomes:**

- 1) Safety of HCL therapy compared to SAPT in women with T1D throughout gestation and the early post-partum period assessed through episodes of severe hypoglycemia and time spent with glucose <54 mg/dL.
- 2) Indices of glucose control and fear of hypoglycemia in pregnant women with T1D using HCL or SAPT therapy throughout pregnancy and early post-partum. Indices of glucose control are time spent in the glucose target ranges <54 mg/dL and <63 mg/dL (hypoglycemia), 63-140 mg/dL (time in range), and >140 mg/dL and >180 mg/dL (hyperglycemia). Fear of hypoglycemia is assessed as behavior, worry, and total scores of fear of hypoglycemia determined by the Hypoglycemia Fear Survey.

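### The Specific Aim 2 power statement calls 3.3 hours/day with an SD of 2.5 hours/day an effect of 1.0 SD; it is 1.32 SD, and the planned t-test then has about 80% power, not 83%

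*Combined protocol and SAP*

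**What the plan says.** Section IV.F, under Power and Sample Size Calculations, makes its time-in-range claim as follows: "with a sample size of 10 women per group (20 study completers), we will have 83% power to detect a difference in time spent". The outcome meant is glucose within target, and the difference is given as "of 3.3 hours/day (13.8%) between HCL to SAPT, assuming a standard deviation of 2.5 hours/day (effect size=1.0 SD"). The next sentence gives external support: "This is similar to effect sizes reported in another artificial pancreas study showing a difference of 2.5 hours/day (10.4%) between groups". It also cites a crossover study of closed-loop therapy in pregnancy with a difference of 3.6 hours/day (15.2%).

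On the test, the Aim 2 paragraph of the same section plans group comparisons "using t-tests for normally distributed variables and Wilcoxon Rank-Sum test for non-normally distributed variables". On the significance level it says: "The alpha level will be 0.05 for all analyses, except the non-inferiority tests (alpha = 0.025"). It does not say whether the Aim 2 tests are one- or two-sided, and it names no formula or software for the 83%.

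Time in range is one of the primary glucose indices in section IV.A, Primary Outcomes: "63-140 mg/dL (time in range), and >140 mg/dL and >180 mg/dL (hyperglycemia").

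**The concern.** A standardised effect size is the difference divided by the standard deviation. The sentence gives all three quantities, and they do not fit together. Either the label is wrong, or one of the inputs is wrong and the power with it. The reader cannot tell which without redoing the calculation.

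Two things are at stake. First, the 83% is the only statement of what the trial can show on time in range, so it should follow from its inputs and from the planned test. Second, the label invites a misreading. With an SD of 2.5 hours/day, an effect of 1.0 SD is exactly 2.5 hours/day, and that is the first of the two external differences the next sentence calls similar. A reader could conclude that 10 women per group give 83% power for 2.5 hours/day. The trial is meant to supply planning data for a larger one, and the standardised effect is a figure a later planner might well reuse.

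**Working it through.** **Inputs, all from section IV.F except where noted**
- n = 10 completers per group. Drop-out is already allowed for, since the calculation uses completers.
- Difference 3.3 hours/day, also given as 13.8% of the day.
- SD 2.5 hours/day.
- Alpha 0.05, taken as two-sided. This is an assumption; one-sided is shown below.
- Test: two-sample t-test if the data are normal.

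**Step 1: do the inputs agree with each other?** 3.3/24 = 13.75%, which matches 13.8%. The hours and the percentage are consistent.

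**Step 2: the effect size.** d = 3.3/2.5 = 1.32. Over rounding of both inputs, d runs from 3.25/2.55 = 1.27 to 3.35/2.45 = 1.37. The 13.8% narrows this further: 13.75% to 13.85% of 24 hours is 3.30 to 3.32 hours, so d runs from 3.30/2.55 = 1.29 to 3.324/2.45 = 1.36. Neither range includes 1.0.

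**Step 3: reproduce the 83%.** For two groups of 10 the noncentrality is d × √(10/2) = d × √5.
- Normal approximation: power = Φ(d√5 − 1.96). At d = 1.32, d√5 = 2.952, so power = Φ(0.992) = 83.9%.
- t-test: noncentral t with 18 degrees of freedom, critical value 2.101, noncentrality 2.952. Power = 79.7%. A simulation of 200,000 trials also gave 79.7%.

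| Effect (SD 2.5 h/day) | t-test, two-sided 0.05 | Normal approximation |
|---|---|---|
| 3.3 h/day, d = 1.32 | 79.7% | 83.9% |
| Wide rounding range, d = 1.27 to 1.37 | 76.9% to 82.4% | 81.3% to 86.4% |
| Range narrowed by the 13.8%, d = 1.29 to 1.36 | 78.1% to 81.8% | 82.5% to 85.9% |
| 2.5 h/day, d = 1.00 | 56.2% | 60.9% |
| 3.6 h/day, d = 1.44 | 86.1% | 89.6% |

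One-sided alpha 0.05 at d = 1.32 gives 88.4% (t-test) or 90.4% (normal approximation), neither of which is near 83%. One-sided at d = 1.0 gives 69.4% or 72.3%.

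**Step 4: what effect would give exactly 83%?** d = 1.303 by normal approximation and d = 1.378 by t-test. The first lies inside the rounding range of the inputs; the second lies outside it. At d = 1.0 the t-test would need about 18 per group for 83%.

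The 83% was therefore computed at roughly 1.3 SD, and the 1.0 SD label is wrong. Of the calculations tried, only the two-sided normal approximation comes within rounding of 83%. The planned t-test does not reach it for any rounding of the stated inputs.

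**The case against.** The division is not in dispute. The case on the other side concerns what else is drawn from it.

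- **The normal approximation is an inference.** At the stated inputs it gives 83.9%, which would be printed as 84%, and the plan names no method. The Aim 1 statement in the same paragraph does not suggest a normal approximation: a margin of 1.5, SD 1.1, 10 per group and one-sided 0.025, with a true difference of zero assumed, give 82.2% by t-test and 86.2% by normal approximation, against a stated 80%. This stands. The approximation is a possible explanation and should not be reported as the authors' method.
- **The gap is small.** About 3 points, in a pilot with a fixed target of 20 completers, and power stays near 80%. This also stands, and it limits the weight of the point. It does not make the printed figures right.
- **The 2.5 hours/day remark is one-sided.** The plan ties 83% to 3.3 hours/day only, and the two cited differences, 2.5 and 3.6 hours/day, lie on either side of it. This is fair. If power is quoted for one, it should be quoted for both: about 56% and 86%.
- **The test and its sidedness are not settled.** Two-sided is assumed, and a Wilcoxon test replaces the t-test if the data are not normal. Under normality that test has slightly less power, about 78% using its asymptotic efficiency of 3/π. The authors need to confirm the sidedness, but neither alternative yields 83%.

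**Conclusion.** The concern holds. The effect-size label is wrong as written: the stated difference and SD give 1.32 SD, and rounding cannot bring this to 1.0. No other part of the document corrects it.

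The stated power is also a little high for the planned test: 79.7% against 83%, with a range of 78.1% to 81.8% once the 13.8% is used to limit rounding. This rests on 10 completers per group, normal data with a common SD of 2.5 hours/day, and two-sided alpha 0.05, the last being an assumption.

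The consequence is modest. The trial is not shown to be underpowered for 3.3 hours/day. The wrong label matters mainly because it could be read as 83% power for a 1.0 SD effect, where the t-test has 56%. The sentence should be corrected; nothing in the design depends on it.

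**What to change.** Replace the Aim 2 power sentence with wording to this effect: *With 10 completers per arm, a two-sided two-sample t-test at alpha 0.05 has about 80% power for a mean difference of 3.3 hours/day (13.8% of the day) if the SD is 2.5 hours/day, a standardised effect of 1.32.* The authors should confirm that a two-sided test is meant.

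If they prefer to keep 83%, they should state the method that produced it, and say so if it was a normal approximation. The label must change to 1.32 SD either way, unless one of the inputs proves to be the error, in which case the power must be recalculated.

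Optionally, add the t-test power for both cited differences at the same SD: about 56% for 2.5 hours/day and about 86% for 3.6 hours/day. That removes any suggestion that 83% applies to the smaller one.

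The cost is a wording change in one sentence and a stated power about 3 points lower. Sample size, test, data collection and analysis stay as they are.

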##### **B. Description of Population to be Enrolled:**

We anticipate recruiting women with T1D for at least a year who are pregnant (11 weeks gestation or earlier) between the ages of 18 and 45 years old. We expect to screen up to 37 individuals, randomize up to 24 women, and have 20 completers (10 women per group).

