be asked to calibrate per device instructions, log self-monitored glucose values (7 per day), insulin doses, carbohydrate intake, and exercise. Women who are compliant with device wearing and log sheets, who do not have an adverse reaction to device adhesives or wearing, who are willing to wear the study devices, and who are otherwise deemed appropriate candidates by the study PI will be invited to continue in the study (see Figure 1). The operational definition of compliance for the run-in phase is device wearing for  $\geq 80\%$  of time during the run-in phase, changing infusion sets every 3-4 days, performance of a minimum of 2 finger-sticks per day (as the HCL system requires 2-4 calibrations per day), filling out  $\geq 80\%$  of the log sheets, successful remote uploading of the CGM data, and communication with the study team during the run-in phase. Women will also be asked to record dietary (food and beverage) intake for three days during the run-in phase using log sheets. Food records will be reviewed to assess dietary compliance with the personalized pregnancy nutrition goals provided to participants and carbohydrate counting skills. Targeted enrollment after the run-in phase will be 28 women and by the end of the study will be 20 women (10 completers per group allowing for a drop-out rate of 36% due screen failures, miscarriages, dropping out, or subjects being lost to follow up).

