#### **G. Summarize Knowledge to be Gained:**

This would be the first study to compare an FDA-approved HCL system to SAPT throughout pregnancy and the early post-partum period. Women across the USA are already using the HCL system being investigated in this proposal, and most pregnancies are unplanned, thus there are likely many women getting pregnant while on HCL therapy without knowing its effects on gestation. This study would demonstrate if the HCL system is safe in pregnancy. This study would provide pilot data to design and implement a larger, randomized controlled trial with adequate power to detect differences in maternal and fetal outcomes.

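### Aim 4 is meant to give estimates for a larger trial, but its main analysis is chi-square tests on about 10 women per arm, with no risk difference or confidence interval planned

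*Combined protocol and SAP*

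**What the plan says.** Section F, Power and Sample Size Calculations, states that "this study is not powered to detect significant differences in maternal-fetal outcomes" and gives the purpose of Aim 4 instead: "our goal is to provide estimates and preliminary data on these outcomes to inform the sample size needed for a larger trial". Section G repeats the purpose for the study as a whole: "This study would provide pilot data to design and implement a larger, randomized controlled trial with adequate power to detect differences".

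Section F, Statistical Analysis Plan, gives the Aim 4 method: "we will examine rates of fetal loss, preeclampsia, cesarean section, LGA, and neonatal hypoglycemia using Chi-square tests". It adds an adjustment for unequal follow-up "using Poisson regression with an offset for follow-up time as a sensitivity analysis, in addition to the proposed chi-square tests". The aim is labelled exploratory.

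Hypotheses SA 4.1 and SA 4.2 in section II expect these outcomes to occur at similar rates in the two arms.

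The number of women is set by Aim 1: "With a sample size of 10 women per group (20 study completers), we will have 80% power to detect non-inferiority". Section B allows up to 24 randomized and section C gives 28 women after the run-in, so Aim 4 could have between 10 and 14 women per arm.

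No confidence interval, risk difference or pooled rate is specified for any Aim 4 outcome. Nothing says which estimate would feed the design of the larger trial.

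**The concern.** The stated goal and the main method do not match. The goal is estimation, and the method is a significance test. A p-value is not something a sample-size calculation can use.

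The test does not serve the hypotheses either. They predict similarity, and a non-significant result on 10 women per arm is the likely outcome whether or not the arms differ. Reported alone, it could be taken as evidence that maternal and fetal outcomes are alike under the two therapies, when the data would also be compatible with large differences in either direction.

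What is at stake is the usefulness of the pilot data for the next trial and the way an unpowered comparison will be read. The sample size, primary outcomes and safety rules of this trial are not affected.

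**Working it through.** **1. The plan's own figure.** No size, power or precision is given for Aim 4; the 10 per arm comes from Aim 1. With margin 1.5, SD 1.1, one-sided alpha 0.025 and 80% power, n = 2(1.96 + 0.84)² × 1.1² / 1.5² ≈ 8.4, so 9 per arm by the normal formula. By the noncentral t, power is 77.5% at 9 and 82.2% at 10, so 10 is the smallest number reaching 80%. The figure reproduces, but it says nothing about binary pregnancy outcomes.

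**2. Event rates (assumption).** Section III, Background and Significance, reports for a crossover study of 16 women: preeclampsia 5/16 = 31%, cesarean 15/16 = 94%, LGA 13/16 = 81%, neonatal hypoglycemia 14/16 = 88%. Of these women, 14 of 16 continued closed-loop therapy to delivery, so these are not SAPT rates. They serve only to show scale. No fetal-loss count is given there.

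**3. Precision.** Half-width for an arm difference is 1.96 × √(2p(1−p)/10); for a rate pooled over 20 women it is 1.96 × √(p(1−p)/20). The smaller expected count per arm is 10 × min(p, 1−p).

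| Outcome | p | Arm difference, 10 per arm | Pooled rate, 20 women | Smaller expected count per arm |
|---|---|---|---|---|
| Preeclampsia | 0.3125 | ±41 points | ±20 | 3.1 |
| LGA | 0.8125 | ±34 | ±17 | 1.9 |
| Neonatal hypoglycemia | 0.875 | ±29 | ±15 | 1.3 |
| Cesarean | 0.9375 | ±21 | ±11 | 0.6 |

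These simple (Wald) half-widths are rough at such small counts. At 14 per arm the arm-difference column shrinks by √(10/14) = 0.845, to about ±18 to ±34 points. For fetal loss, an arm with 0 events in 10 has an exact 95% interval of 0 to 31%.

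**4. What the chi-square test can do.** Suppose the true LGA rates were 81% and 66%, an assumed 15-point difference. Enumerating all 11 × 11 outcomes at 10 per arm, the uncorrected chi-square test reaches p < 0.05 about 9% of the time. Non-significance is therefore expected even with a difference of that size. All the smaller expected counts in step 3 are also low enough to make the chi-square approximation unreliable.

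**5. If the observed difference were used to size the next trial.** This is conditional, because the documents do not plan it. The same enumeration puts each pilot's observed LGA rates into the two-proportion formula, n per arm = [1.96√(2p̄(1−p̄)) + 0.84√(p₁(1−p₁) + p₂(1−p₂))]² / (p₁−p₂)², where p̄ is the mean of p₁ and p₂. True power is then evaluated at that n. For 81.25% versus 66.25%, the number truly needed is 134 per arm.

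| Assumed true LGA reduction | Zero or reversed difference, or planned trial with true power under 50% |
|---|---|
| 10 points | 81% of pilots |
| 15 points | 70% (30.1% zero or reversed; 40.2% under 50% power) |
| 20 points | 62% |
| 25 points | 49% |

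In the 15-point case, 18.7% of pilots would plan a trial with at least 80% true power. With 12 or 14 per arm the 70% becomes 65% or 62%. At 10 per arm and a 15-point reduction, preeclampsia and neonatal hypoglycemia give 63% and cesarean 65%.

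**The case against.** The best defence is that Aim 4 is already labelled exploratory and unpowered, that no primary conclusion depends on it, and that a 2×2 table behind a chi-square test already contains the per-arm and pooled proportions. The Poisson model would also yield a rate ratio with a standard error. This stands in part: the inputs exist, and the gap is in what is specified and reported. But the plan commits to no interval for either analysis, and intervals are what its declared purpose needs.

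A reader might infer several stronger things that the documents do not support:

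- **That Aim 4 is analysed by chi-square tests alone.** Section F says rates will be examined and adds the Poisson sensitivity analysis.
- **That the next trial will be sized from the observed arm difference.** No section says so, and the hypotheses expect no difference to carry forward.
- **That about 70% of such pilots mislead.** That figure belongs to one assumed scenario: LGA, a 15-point effect, 10 per arm, and the definition of failure used above. It moves with each of these.
- **That sizing from the pooled rate plus a fixed difference has been shown to be better.** With a fixed 15-point difference and a true difference of 15 points, median true power is 79%, but that method has been handed the true effect. If the true LGA difference were 10 points, median true power would be 47%; at 5 points, 15%.

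**Conclusion.** The point holds as a mismatch between purpose and method. Aim 4 is declared to be about estimation, yet its main analysis is a set of tests that, at about 10 women per arm, cannot support similarity and cannot inform a sample size. The uncertainty that would go unreported is roughly ±21 to ±41 points for an arm difference. That rests on borrowed rates from 16 women who were mostly on closed-loop therapy, and on a rough interval formula.

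This is a specification gap in an exploratory aim. It is not an error in the trial's sample size. The scenario figures for sizing from the observed difference (about 80% down to 50% as the assumed LGA reduction rises from 10 to 25 points) support a caution only, and the conclusion does not depend on them.

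**What to change.** In section F, Statistical Analysis Plan, Specific Aim 4, make the main analysis per-arm and pooled proportions for each of the five outcomes, and the HCL minus SAPT risk difference with a 95% score or Newcombe interval, labelled exploratory. These replace the chi-square p-values. The Poisson regression can stay as the sensitivity analysis.

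Optionally, add a sentence to Power and Sample Size Calculations that the observed arm difference will not be taken as the design effect for the larger trial.

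The cost is SAP wording only, with no change to data collection or sample size. The small downside is giving up p-values for five outcomes that the study says it is not powered to compare.
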